## 6.0 ENROLLMENT PROCEDURES

To enter a patient, the Investigator or Study Team will contact the Clinical Research Services' (CRS) Representative. All eligibility requirements must be reviewed prior to the patient entering the study. The following information must be provided to the CRS Representative:

- 1) Completed and signed protocol-specific eligibility checklist;
- 2) All pages of the original signed informed consent form (ICF) including HIPAA Form B;
- 3) Relevant source documents including but limited to: subject medical history and physical exam, concomitant therapy, admission or discharge notes, diagnostic reports, pathologic confirmation of diagnosis, and relevant subject-specific written communication.

### 6.1 Cancellation Guidelines

If a patient does not receive protocol therapy, the patient may withdraw. Contact the CRS Representative, or e-mail the information including the reasons for withdrawal within 10-business days.

### 6.2 Emergency Registration

If an emergency registration takes place after business hours, the items listed above must be submitted by the next business day.

### 6.3 Enrollment Procedure(s)

[figure not shown]
After all Enrollment Guidelines are met as described (above) a CRS Clinical Research Coordinator (CRC) will enroll the patient by entering the requisite information into the informatics software system (e.g. CIERRA) developed by the SCCC-Informatics Office to implement enrollment. This system will automatically generate a secure e-mail message to the appropriate study team members, i.e. CRC, CRORS, and the Research Pharmacist(s).

**Study treatment must be initiated within seven (7) days of enrollment.**

## 7.0 STUDY DESIGN

The study will be a single-institution, open-label, single-arm phase II study. Since the primary endpoint is survival outcome (PFS) sample size calculation is based on a single-arm survival design. We will employ early stopping rules for lack of efficacy, based on previously reported historical controls (19% PFS at 3 months) and a large database suggesting that a progression-free rate at 3 months of >40% correlates with an active drug in the second-line setting for patients with advanced sarcoma (43). Patients will be treated with twice daily dosing of axitinib alone for the first 7 days, followed by concurrent axitinib administered twice daily at 5 mg PO twice daily, plus intravenous administration of pembrolizumab every 21 days (Figure 3). Patients will be assessed every three weeks for toxicity. After the first five patients are enrolled, we will assess safety of the combination. If 2 or fewer patients exhibit DLT, we will

then proceed with inpatient titration of axitinib dosing at each cycle based on the presence or absence of predefined toxicities (Section 7.1, Table 3). Correlative studies characterizing T-cells in tumor tissue and in peripheral blood will be performed at three timepoints: 1. pre-treatment, 2. on-treatment on cycle 3 day 1, and 3. off-study. Additional exploratory imaging investigations, and assessment of circulating tumor cells are included for all patients (See Appendix F for complete description of correlative studies).

**Figure 3. Schematic diagram of the study.** The first cycle of treatment will be seven weeks, with one week of axitinib alone prior to initiation of pembrolizumab. Subsequently, six-week cycles of treatment consist of twice daily oral doses of axitinib administered continuously with intravenous (I.V.) administration of pembrolizumab on day 1 and 22. The first five evaluable patients will be considered a safety lead-in, and will not have axitinib dose escalation above 5 mg PO bid. If 2 or fewer patients in the safety lead-in develop DLT, axitinib will then be individually titrated based on toxicity beginning on cycle 2 day 1.

### 7.1 Axitinib Dose Titration with Flat Dose of Pembrolizumab

In trials with dose escalation of pembrolizumab, no difference in response nor toxicity was noted in melanoma patients randomized to either 2 mg/kg every three weeks versus 10 mg/kg every three weeks (44) [4]. Thus, this trial will utilize flat dosing of pembrolizumab based on equivalent pharmacokinetics with 200 mg flat dose compared to FDA approved dose of 2 mg/kg (Merck, Investigators Brochure). However, increasing response rates were noted in patients who were escalated on axitinib therapy (17) [5]. Given the younger age in general of sarcoma patients and lack of other comorbid medical conditions, we will incorporate individualized dose titration of axitinib based on toxicity to maximize exposure and likelihood of response. Dose levels are summarized in Table 3. See Section 10.2 for toxicity criteria and dose titration rules.

Dose Level	Axitinib dose	Pembrolizumab dose
-3	2 mg PO bid	200 mg flat dose *
-2	3 mg PO bid	
-1	4 mg PO bid	
1 (Starting dose level)	5 mg PO bid (FDA-approved)	
2	6 mg PO bid	
3	7 mg PO bid	
4	8 mg PO bid	
5	10 mg PO bid (maximum)	

**Table 3. Axitinib Dose Levels.** \*Fixed dose based on simulations of population PK model for pembrolizumab suggesting consistency with previous 2 mg/kg dose (see Merck Investigator’s Brochure for pembrolizumab).

Based on the recently completed dose escalation trial of concurrent axitinib and pembrolizumab in renal cell carcinoma, estimated DLT rate is 30%. Thus, we will conduct a safety review after the first 5 patients enrolled on the study during the first stage to ensure similar rates of DLT are noted in our patient population.

### 7.2 Dose-Limiting Toxicity (DLT)

Dose-Limiting Toxicity (DLT) is defined as any one of the following Adverse Events (AEs) that occurs during the first cycle (49 days) and is considered by the Investigator to be related (possible, probable, or definite) to study drug, specifying attribution to axitinib, pembrolizumab, or both. Management and dose modifications associated with the above AEs are outlined in Section 10.0 (Treatment/Dose Modifications).

DLT is defined as any one of the following (Table 4 and 5):

#### Lab Toxicity

AE	Patient Population	Dose Limiting Toxicity
Anemia (Hemoglobin)	All	<6.5 g/dl
Platelet count decreased	All	Grade 4 (<25,000mm  )
Febrile neutropenia	All	≥ Grade 3
Acute kidney injury	Does not resolve within 7 days	≥ Grade 3 (>3 x above baseline)
Proteinuria	Does note resolve within 7 days	≥ Grade 3
Liver function abnormalities (transaminitis/hyperbilirubinemia)	If grade 2 (>1.5 - 3.0 x ULN ) at baseline, than any ≥50% increase from baseline that does not resolve within 7 days	>5 x ULN

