**Table 5. Summary of Non-Lab DLTs.**

### 8.0 TREATMENT PLAN

A cycle of treatment will consist of concurrent axitinib and pembrolizumab therapy for 6 weeks (Figure 3, Table 6), except for cycle 1 which will be 7 weeks as detailed above. Administration of axitinib shall occur continuously with pembrolizumab administered on day 8 and day 29 of the first cycle, and days 1 and 22 of the following cycles. The first five patients will not be dose-escalated above 5 mg PO twice daily axitinib. If these patients exhibit acceptable rates of DLT, starting with patient 6, dose-escalation of axitinib will be permitted. No dose escalations will be permitted during cycle 1. On day 1 of cycle 2 and the subsequent cycles, dose escalation of axitinib is permitted if toxicity is within the specified criteria. No dose-escalation will be conducted in the middle of any cycle. Dose reduction or interruption is permitted in the case of toxicity at any time as per section 10.0.

Trial treatment should be administered after all procedures/assessments have been completed as detailed in Section 12.0. Trial treatment may be administered up to 3 days before or after the scheduled Day 1 of each cycle due to administrative (e.g. scheduling) reasons.

Cycle(s)	1							2						Imaging prior to every subsequent odd cycle (i.e. 3, 5, 7, 9, etc.)	3, 4, 5, etc. until progression					
	1	2	3	4	5	6	7	1	2	3	4	5	6		1	2	3	4	5	6
Week(s)	1	8	1	2	2	3	4	1	8	1	2	2	36	1	8	1	2	2	3	
Day(s)	1	8	5	2	9	6	3	1	8	5	2	9	36	1	8	5	2	9	6	
Axitinib oral, BID continuously (uptitration permitted starting from cycle 2)	X	X	X	X	X	X	X	X	X	X	X	X	X	X	X	X	X	X	X	
Pembrolizumab IV q21 days		X			X			X			X			X			X			

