#### Proteinuria

In a controlled clinical study with **INLYTA** for the treatment of patients with RCC, proteinuria was reported in 39/359 patients (11%) receiving **INLYTA** and 26/355 patients (7%) receiving sorafenib. Grade 3 proteinuria was reported in 11/359 patients (3%) receiving **INLYTA** and 6/355 patients (2%) receiving sorafenib.

Monitoring for proteinuria before initiation of, and periodically throughout, treatment with INLYTA is recommended. For patients who develop moderate to severe proteinuria, reduce the dose or temporarily interrupt INLYTA treatment.

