### 12.2.1 Cycle 1, day 1 ( $\pm 3$ days) – CTU visit

The following assessments should be performed on Cycle 1, day 1:

- PE
- ECOG PS
- V/S
- Weight
- CBC with differential

- CMP, Mg, Phosphate, direct bilirubin
- UA
- Urine pregnancy test (repeat only if not done within 7-days prior)
- Imaging studies (repeat only if screening imaging scans are deemed inadequate as per Radiology, i.e. missing fat suppression, contrast-enhancement, otherwise inadequate views, or performed outside of the 28 day window)
- Correlative studies: peripheral blood collection – see Section 13.0

12.2.2 Cycle 1, day 8 ( $\pm 3$  days) – CTU visit (Pembrolizumab administration)

The following assessments should be performed on Cycle 1, day 8:

- PE
- ECOG PS
- V/S
- Weight
- Patient dosing diary review and BP logs
- CBC with differential
- CMP, Mg, Phosphate, direct bilirubin
- Urine pregnancy test
- 12 lead EKG
- **Correlative studies: peripheral blood collection – see Section 13.0 (additional sample for expansion cohort)**

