12.2.8 Cycle 2, day 1: CTU visit, Pembrolizumab administration

The following assessments should be performed on Cycle 2, day 1:

- Collection of previous cycle's patient dosing diary and BP log
- PE
- ECOG PS

- V/S
- Weight
- CBC with differential
- CMP, Mg, Phosphate, direct bilirubin
- Coagulation factors
- TFTs (T3, T4 and TSH)
- UA (if protein 2+ or greater (grade 2) with no evidence of infection or contaminated sample, obtain urine microalbumin and urine creatinine clearance)
- Urine pregnancy test
- Consider axitinib dose escalation (see Section 10.2)

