12.7 Calendar of Clinical and Laboratory Evaluations (continued on following page)

Cycle	Screening	1							2						3		Subsequent Cycles	Off Treatment (treatment discontinuation)	EoT Safety Evaluation	Follow-up A	Survival
		1	2	3	4	5	6	7	1	2	3	4	5	6	1	4 F					
Week (per Cycle)		1	2	3	4	5	6	7	1	2	3	4	5	6	1	4 F	Weeks 1 and 4 F,I,J	(EOT) ±7 days	30 days (±5 days) after EOT	Q12 Weeks (±7 days)	Q12 Weeks (±7 days)
Day (±3d per Cycle)	-28 to 0	1	8	15	22	29	36	43	1	8	15	22	29	36	1	22 F	Days 1 and 22 F				
ICF	X																				
Eligibility	X																				
Demographics	X																				
Medical history	X																				
PE	X	X	X	X	X	X	X	X	X	X	X	X	X	X	X		X (Day 1)	X	X	X	
ECOG PS	X	X	X	X	X	X	X	X	X	X	X	X	X	X	X		X (Day 1)	X	X	X	
Height	X																				
Weight	X	X	X	X	X	X	X	X	X	X	X	X	X	X	X		X (Day 1)	X	X	X	
V/S (BP, HR, RR, oral temp, and O 2 sat)	X	X	X	X	X	X	X	X	X	X	X	X	X	X	X		X (Day 1)	X	X	X	
CBC, diff	X	X	X	X	X	X	X	X	X	X	X	X	X	X	X	X	X (Days 1, 22)	X	X	X	

A For those patients without documented evidence of objective disease progression, the same imaging studies used at Baseline/Screening; not required at Off-Treatment, if reason for ‘off study’ is radiographic progression.

Cycle	Screening	1							2						3		Subsequent Cycles	Off Treatment (treatment discontinuation)	EoT Safety Evaluation	Follow-up A	Survival
		1	2	3	4	5	6	7	1	2	3	4	5	6	1	4 F					
Day (±3d per Cycle)	-28 to 0	1	8	15	22	29	36	43	1	8	15	22	29	36	1	22 F	Days 1 and 22 F				
CMP, Mg, PO4, direct bilirubin	X	X	X	X	X	X	X	X	X	X	X	X	X	X	X	X	X (Days 1, 22)	X	X	X	
PT/INR, aPTT	X								X						X		X (Day 1)	X	X	X	
TFTs (T3, T4, TSH)	X								X						X		X (Day 1)	X	X	X	
Urine pregnancy	X	X B	X			X			X			X			X	X	X (Days 1 and 22)	X	X	X	
U/A (micro-albumin and Cr Clearance, if > 2+ protein without other cause)	X	X							X						X		X (Day 1)	X	X	X	
12-Lead ECG	X		X			X						X C				(X) C	X C (Day 22 C )	X			
2D ECHO	X																	X			

B Repeat only if not done within previous 7 days.

C Perform only if axitinib dose escalation performed on day 1 of current cycle.

Cycle	Screening	1							2						3		Subsequent Cycles	Off Treatment (treatment discontinuation)	EoT Safety Evaluation	Follow-up A	Survival
		1	2	3	4	5	6	7	1	2	3	4	5	6	1	4 F					

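### Proteinuria is a first-cycle DLT, but no post-dose urinalysis is scheduled before cycle 2 day 1 (nominal day 50), so this part of the reported DLT count is biased downward

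*Combined protocol and SAP*

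**What the plan says.** Section 7.2 restricts a DLT to a listed, treatment-related event that "occurs during the first cycle (49 days" (the bracket closes there). The proteinuria row of Table 4 sets the threshold at grade 3 or higher, with the qualifier "Does note resolve within 7 days"; *note* is plainly a misprint for *not*.

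Section 8.0 makes cycles six weeks long, "except for cycle 1 which will be 7 weeks as detailed above". It also places each visit's assessments before treatment and allows 3 days either side of day 1 of a cycle.

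Section 12.2.1 includes urinalysis under "The following assessments should be performed on Cycle 1, day 1". The lists for days 8, 15, 22, 29, 36 and 43 (Sections 12.2.2 to 12.2.7) do not. It returns in Section 12.2.8, cycle 2 day 1, as "UA (if protein 2+ or greater (grade 2) with no evidence of infection or contaminated sample", which triggers quantification. The calendar row in Section 12.7, "U/A (micro-albumin and Cr Clearance, if > 2+ protein without other cause", is marked at screening, cycle 1 day 1, cycle 2 day 1, cycle 3 day 1 and day 1 of later cycles.

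Section 17 monitors treatment-related DLTs as unacceptable toxicity and describes a period running to one month after treatment ends. Section 16.3 reports the number of patients with DLT.

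On background risk, Section 9.1.4 says of the renal cell carcinoma study: "Grade 3 proteinuria was reported in 11/359 patients (3%) receiving INLYTA".

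**The concern.** A toxicity that is found only by a test can be counted only if the test is done inside the counting window. Proteinuria is such a finding, and after dosing starts its test is not scheduled until the window has nominally closed. Followed as written and on time, the schedule returns zero for this component whatever the true rate.

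The other laboratory rows of Table 4 do not share the problem. Blood counts and chemistry are drawn weekly through cycle 1, and acute kidney injury, which carries the same 7-day condition, has weekly chemistry behind it. At stake is whether the reported DLT rate describes what Section 7.2 says it describes.

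**Working it through.** **1. The window.** 7 weeks x 7 days = 49 days, which reproduces the figure in Section 7.2. Cycle 2 day 1 is therefore study day 49 + 1 = 50. With 3 days either way it falls on day 47 to 53.

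**2. Scheduled tests against the window.** The visit lists and the calendar agree.

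| Visit | Nominal day | Blood count and chemistry | Urinalysis |
|---|---|---|---|
| Cycle 1 day 1 (before dosing) | 1 | yes | yes |
| Cycle 1 days 8, 15, 22, 29, 36, 43 | 8 to 43 | yes, each visit | none |
| Cycle 2 day 1 (before that day's treatment) | 50 | yes | yes |

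None of the six post-dose cycle 1 visits includes urinalysis. The urinalysis text and the calendar differ slightly on when quantification is triggered (2+ or greater, against more than 2+), but that does not affect this point.

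**3. Can a scheduled test register the DLT?**
- At the nominal date: 50 > 49, so no.
- Visit brought forward to day 47, 48 or 49: proteinuria could be found in the window. Seven days later is day 54, 55 or 56.
- If persistence had to be settled by day 49, detection would be needed by 49 - 7 = day 42, and no post-dose test is scheduled by then. Section 7.2 does not state that requirement. It asks only that the event occur in the first cycle, so an early visit with persistence judged afterwards could qualify.

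**4. Size.** The current urinalysis schedule mainly concerns the alveolar soft part sarcoma expansion, up to 10 patients (Section 1.5). Assume the rate in Section 9.1.4 applies to them:
- p = 11/359 = 0.031
- expected cases = 10 x 11/359 = 0.31
- chance of at least one = 1 - (348/359)^10 = 0.27

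Given that rate, both are upper limits: it covers the whole of treatment rather than 49 days, and it carries no 7-day persistence condition. The documents do not give the cycle 1 share.

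**5. Section 7.2 against Section 17.** A grade 3 finding on day 50 lies outside the 49-day window. It lies inside a period that runs to one month after treatment ends. The same event could count in one place and not in the other. Section 17 attaches its period to the word *acute*, which its own definition of unacceptable toxicity does not use, so the intended window is unclear.

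**The case against.** The best defence is that the DLT is not unobservable. Unscheduled testing is not barred, a cycle 2 visit on day 47 to 49 falls inside the window, and a day-50 sample taken before that day's treatment still reflects cycle 1 exposure. Retesting after a grade 3 finding is also implied: Table 11 holds axitinib until grade 1 or lower, and Section 10.1 sets a 3-week limit for resolution. All of this stands, and it rules out saying that the event can never be detected. It leaves the gap at the nominal date, and it does not say whether the cycle 2 day 1 result counts.

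Monitoring on day 1 of each cycle can also be defended as periodic, which is what Section 9.1.4 recommends, and cycle 1 has weekly examination, vital signs and chemistry. That answers a claim that patients go unmonitored; it does not answer the counting problem.

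A reader might infer that the lead-in decision or the stopping table was distorted. Under the Section 17 prior, the posterior probability of a rate above 40% is 0.920 with 4 DLTs in 5 patients and 0.725 with 3 in 5, so one missed event can cross the 90% line. The documents do not support that inference here. Section 17 applies the rule to 30 patients, and Section 1.5 says the first 30 had already accrued. The revision history, used only as background, records that version 4.0 reduced urinalysis to day 1 of each cycle. Those patients may have had more urine tests; their cycle 1 schedule is not shown.

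**Conclusion.** The inconsistency is real and goes beyond missing detail: Table 4 lists a laboratory DLT that, at nominal visit dates, no scheduled test can register within the window set by Section 7.2. The direction of the bias is clear, since an unmeasured component can only lower the count.

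The size is small: at most about 0.3 expected cases and a 27% chance of at least one among up to 10 expansion patients. This assumes that the renal cell carcinoma rate carries over to sarcoma patients on the combination, and that no extra urine tests were done. Applying the same rate to all 40 patients gives 40 x 11/359 = 1.2 cases and a 71% chance of at least one. That figure should not be used, because it spreads the current schedule over patients who accrued before it and uses a whole-treatment rate for a 49-day window.

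An effect on the lead-in or on the 30-patient stopping rule is not shown. The separate conflict between the windows in Sections 7.2 and 17 stands on the text alone.

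**What to change.** Reconcile Section 7.2 with Table 4, Sections 12.2 and 12.7, and Section 17, so that the DLT window and the scheduled urinalysis match and a single counting period is stated. One way is a sentence in Section 7.2 saying that the existing pre-dose cycle 2 day 1 urinalysis, with follow-up to establish persistence, counts toward the cycle 1 DLT assessment, and a matching sentence in Section 17. The misprint in Table 4 can be corrected at the same time.

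This needs no new visit and no new baseline or screening test. Because it relies on a urinalysis already in the schedule, it can also be applied to patients already treated under it, where follow-up results exist. The downside is that the counted DLT rate may rise slightly. Section 11.0 lists a DLT among the reasons treatment may be discontinued, so the sponsor should also make clear whether an event counted this way carries that consequence.

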Renal	
Serum creatinine OR Measured or calculated a creatinine clearance (GFR can also be used in place of creatinine or CrCl)	≤1.5 X upper limit of normal (ULN) OR  ≥60 mL/min for subject with creatinine levels > 1.5 X institutional ULN
Hepatic	
Serum total bilirubin	≤ 1.5 X ULN OR Direct bilirubin ≤ ULN for subjects with total bilirubin levels > 1.5 ULN
AST (SGOT) and ALT (SGPT)	≤ 2.5 X ULN OR ≤ 5 X ULN for subjects with liver metastases
Albumin	≥2.5 mg/dL
Coagulation	
International Normalized Ratio (INR) or Prothrombin Time (PT)	≤1.5 X ULN unless subject is receiving anticoagulant therapy as long as PT or PTT is within therapeutic range of intended use of anticoagulants
Activated Partial Thromboplastin Time (aPTT)	≤1.5 X ULN unless subject is receiving anticoagulant therapy as long as PT or PTT is within therapeutic range of intended use of anticoagulants
a Creatinine clearance should be calculated per institutional standard.	

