**Table 4. Summary of Lab DLTs.**

**Non-Lab Toxicity**

AE	Patient Population	Dose Limiting Toxicity
Rash (acneiform or macro-papular)	All	≥ Grade 3
Palmar-plantar erythrodysethesia syndrome	All	Grade 3
Hypertension	Uncontrollable to less than 150/90 with maximal medical management within 7 days	≥ Grade 3
Bronchopulmonary hemorrhage (hemoptysis)	All	≥ Grade 3
Mucositis oral (Stomatitis)	Non-responsive to maximal supportive medication within 7 days	≥ Grade 3
Other Non-Lab Toxicity	All	≥ Grade 3 with the EXCEPTION of the following: 
 
• nausea, vomiting, diarrhea, constipation or edema controllable with medication within 7 days
 
• grade 3 fever in the absence of infection or neutropenia
 
• tumor flare defined as local pain, irritation or rash localized at sites of known or suspected tumor
 
• transient grade 3 infusion reaction
 
• grade 3 thromboembolic event IF patient is asymptomatic and initiated on anticoagulation – as there is a high prevalence in sarcomas, and this is difficult to attribute to study drug.
 

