Proteinuria	2	Continue treatment if asymptomatic and not associated with creatinine rise. If accompanied by renal insufficiency or evidence of nephritis, refer to pembrolizumab guidelines for treatment and hold axitinib until $\leq$ grade 1.	If isolated proteinuria, no dose reduction. If associated with AKI/nephritis, dose reduce one dose level after resolution to $\leq$ grade 1.
	3	Hold axitinib until $\leq$ grade 1. Refer to pembrolizumab guidelines as per grade 2.	Dose reduce one dose level
Elevation of liver enzymes or bilirubin	2/3	Hold axitinib until $\leq$ grade 1. *	Dose reduce one dose level.
	4	Discontinue axitinib	Discontinue axitinib.
Other toxicity	2	Intolerable grade 2 toxicity, may hold axitinib or dose-reduce at physician discretion.	May hold axitinib or dose-reduce at physician discretion.
	3	Hold until resolution to $\leq$ grade 1	Dose reduce one dose level.
	4	Discontinue axitinib	Discontinue axitinib.

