### **II. IRB Expedited Reporting**

- a. All Investigators should also be aware of local Institutional requirements for AE reporting. For more information regarding the IRB policy, please refer to the UM HSRO's Investigator Manual: [http://hsro.med.miami.edu/documents/HRP-103\\_-\\_INVESTIGATOR\\_MANUAL\\_4.11.2014.docx](http://hsro.med.miami.edu/documents/HRP-103_-_INVESTIGATOR_MANUAL_4.11.2014.docx) and the UM HSRO SOP on New Information (HRP-024)  
<https://eprostat.med.miami.edu/eProst/Doc/0/HLJ5OTJVQEH419E0I6QPT3B199/HRP-024%20-%20SOP%20-%20New%20Information.docx>
- b. All AEs that are serious, unanticipated and (at least) possibly related will be reported to the IRB within ten (10) working days of being made known to the PI.

- c. Events that are more frequent than anticipated or more severe than expected must be reported to the IRB within ten (10) working days of being made known to the PI.
- d. All unanticipated deaths must be reported to the IRB within 24 hours of being made known to the PI.

III. Merck Expedited Reporting (Events of Clinical Interest or ECIs)

- a. In addition to the mandatory MedWatch 3500A Form, the PI is also required to comply with all reporting requirements as supplied by the Investigational Drug Sponsor: Merck.
- b. Selected non-serious and serious adverse experiences must be reported to Merck within 24 hours (and within 2 working days to Merck Global Safety) regardless of attribution to study treatment. The AEs listed and any event that meets the criteria for reporting (as noted) in the protocol **Appendix H** (event term and Grade) must be reported regardless of physician-determined causality with study medication and whether or not considered immune-related by the physician (unless otherwise specified). Physicians/study coordinators/designated site personnel are required to record these experiences as events of clinical interest (ECIs) on the Adverse Events/Experience Forms and to provide supplemental information (such as medical history, concomitant medications, investigations, etc.) about the event.
- c. Additional Sponsor Requirements:

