  - For **Grade 2** events, treat with corticosteroids. When symptoms improve to Grade 1 or less, steroid taper should be started and continued over no less than 4 weeks. Replacement of appropriate hormones may be required as the steroid dose is tapered.
  - For **Grade 3-4** events, treat with an initial dose of IV corticosteroids followed by oral corticosteroids. When symptoms improve to Grade 1 or less, steroid taper should be started and continued over no less than 4 weeks. Replacement of appropriate hormones may be required as the steroid dose is tapered.
- **Hyperthyroidism or Hypothyroidism:**

Thyroid disorders can occur at any time during treatment. Monitor patients for changes in thyroid function (at the start of treatment, periodically during treatment, and as indicated based on clinical evaluation) and for clinical signs and symptoms of thyroid disorders.

  - **Grade 2** hyperthyroidism events (and **Grade 2-4** hypothyroidism):
    - In hyperthyroidism, non-selective beta-blockers (e.g. propranolol) are suggested as initial therapy.
    - In hypothyroidism, thyroid hormone replacement therapy, with levothyroxine or liothyronine, is indicated per standard of care.
  - **Grade 3-4** hyperthyroidism
    - Treat with an initial dose of IV corticosteroid followed by oral corticosteroids. When symptoms improve to Grade 1 or less, steroid taper should be started and continued over no less than 4 weeks. Replacement of appropriate hormones may be required as the steroid dose is tapered.
- **Hepatic:**
  - For **Grade 2** events, monitor liver function tests more frequently until returned to baseline values (consider weekly).
    - Treat with IV or oral corticosteroids
  - For **Grade 3-4** events, treat with intravenous corticosteroids for 24 to 48 hours.
  - When symptoms improve to Grade 1 or less, a steroid taper should be started and continued over no less than 4 weeks.
  - An elevated AST or ALT lab value that is  $\geq 3X$  the upper limit of normal (ULN) **and** an elevated total bilirubin lab value that is  $\geq 2X$  the ULN and, at the same time, an alkaline phosphatase lab value that is  $< 2X$  the ULN, as determined by way of protocol-specified laboratory testing or unscheduled laboratory testing.\*

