\*Note: These criteria are based upon available regulatory guidance documents. The purpose of the criteria is to specify a threshold of abnormal hepatic tests that may require an additional evaluation for an underlying etiology. The trial site guidance for assessment and follow up of these criteria can be found in the Investigator Trial File Binder (or equivalent).

- **Renal Failure or Nephritis:**
  - For **Grade 2** events, treat with corticosteroids.
  - For **Grade 3-4** events, treat with systemic corticosteroids.
  - When symptoms improve to Grade 1 or less, steroid taper should be started and continued over no less than 4 weeks.
- **Management of Infusion Reactions:** Signs and symptoms usually develop during or shortly after drug infusion and generally resolve completely within 24 hours of completion of infusion.

**Table H1** below shows treatment guidelines for subjects who experience an infusion reaction associated with administration of pembrolizumab (MK-3475).

NCI CTCAE Grade	Treatment	Premedication at subsequent dosing
Grade 1 Mild reaction; infusion interruption not indicated; intervention not indicated	Increase monitoring of vital signs as medically indicated until the subject is deemed medically stable in the opinion of the investigator.	None
Grade 2 Requires infusion interruption but responds promptly to symptomatic treatment (e.g., antihistamines, NSAIDS, narcotics, IV fluids); prophylactic medications indicated for <=24 hrs	Stop Infusion and monitor symptoms. Additional appropriate medical therapy may include but is not limited to: 
 
IV fluids
 
Antihistamines
 
NSAIDS
 
Acetaminophen
 
Narcotics
 
 Increase monitoring of vital signs as medically indicated until the subject is deemed medically stable in the opinion of the investigator.	Subject may be premedicated 1.5h (± 30 minutes) prior to infusion of pembrolizumab (MK-3475) with:  Diphenhydramine 50 mg po (or equivalent dose of antihistamine).  Acetaminophen 500-1000 mg po (or equivalent dose of antipyretic).

NCI CTCAE Grade	Treatment	Premedication at subsequent dosing

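### Table 4's single liver cut-off leaves a bilirubin rise to >3.0–5.0 x ULN, from a baseline of ≤1.5 x ULN, outside the DLT definition as a laboratory value

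*Combined protocol and SAP*

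**What the plan says.** Section 7.2 defines a DLT as a related event in the 49-day first cycle that appears in Table 4 (laboratory) or Table 5 (non-laboratory). The list is closed.

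Table 4 gives transaminases and bilirubin a single row. Its population column reads "If grade 2 (>1.5 - 3.0 x ULN ) at baseline, than any ≥50% increase from baseline that does not resolve within 7 days", and its DLT column gives >5 x ULN. Table 5 ends with a grade 3 catch-all, but that row is labelled "Other Non-Lab Toxicity".

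Four other places bear on the row:

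- **Section 5.1, Table 2.** Total bilirubin must be ≤1.5 x ULN, or else "Direct bilirubin ≤ ULN for subjects with total bilirubin levels > 1.5 ULN". AST/ALT must be ≤2.5 x ULN, or "≤ 5 X ULN for subjects with liver metastases".
- **Section 16.2, Endpoints.** DLT is described as related toxicity of grade 3 or higher, with the detail left to Section 7.2.
- **Section 10.2, note under Table 11.** For a patient who starts with grade 2 liver tests, a 50% rise lasting beyond 7 days is to be treated as grade 3.
- **Section 10.3, Table 12.** Grade 2 bilirubin withholds pembrolizumab, and grade 3 or 4 stops it permanently. Footnote 2 uses 5 x ULN as a recovery level for AST/ALT.

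**The concern.** One cut-off has been applied to two tests that the protocol does not treat alike. The row places the top of grade 2 at 3.0 x ULN, yet a patient who starts at or near normal bilirubin has to pass 5 x ULN before the row can count the event. Between those values lies a laboratory event that is above grade 2 on the row's own scale and ends one of the two study drugs under Table 12, but does not carry the DLT label.

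Two things in the analysis depend on that label. The number of patients with DLT is a named secondary safety result (Sections 16.2 and 16.3). The exclusion rule in Section 16.2 also removes from the efficacy analyses those who drop out before completing cycle 1, unless the reason was DLT or clinical progression. A patient who left in cycle 1 with bilirubin at 4 x ULN would lack that DLT exception. The separate requirements for the response analysis set (80% of axitinib doses, two pembrolizumab infusions, a post-baseline assessment) may exclude some such patients anyway.

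**Working it through.** The plan states no figure for this row, so there is none to reproduce. The check is whether any reading of the row counts the event.

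**Inputs.** Baseline band >1.5–3.0 x ULN, relative rise ≥50% unresolved at 7 days, and cut-off >5 x ULN (Table 4); entry limits (Table 2). Let b be baseline bilirubin and v the on-study value, both in multiples of ULN, with v sustained beyond 7 days.

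**Readings of the two columns**

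- (a) Alternatives: v > 5, or 1.5 < b ≤ 3.0 with v ≥ 1.5b.
- (b) Both required: 1.5 < b ≤ 3.0, v ≥ 1.5b and v > 5.
- (c) The row applies only to raised baselines: 1.5 < b ≤ 3.0 and v > 5.
- (d) The relative rule for raised baselines and v > 5 for everyone else.

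**Result.** With b ≤ 1.5 the band condition is false, and with v ≤ 5.0 the cut-off is not passed. Every reading therefore returns no DLT. A grid confirms it: b from 0.2 to 1.5 in steps of 0.1 (14 values) and v from 3.1 to 5.0 in steps of 0.1 (20 values) gives 14 × 20 = 280 combinations, of which 0 are DLTs under each reading. With a line at >3.0 for b ≤ 1.5, all 280 are.

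| Baseline to value (x ULN) | Rise | (a) | (b) | (c) | (d) | With added line |
|---|---|---|---|---|---|---|
| 1.0 to 4.9 | 4.9/1.0 − 1 = 390% | no | no | no | no | yes |
| 1.5 to 5.0 | 5.0/1.5 − 1 = 233% | no | no | no | no | yes |
| 2.0 to 3.0 | 3.0/2.0 − 1 = 50% | yes | no | no | yes | unchanged |
| 3.0 to 4.5 | 4.5/3.0 − 1 = 50% | yes | no | no | yes | unchanged |

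Under (a) and (d) the ordering is inverted: a patient ending at 3.0 counts, while one ending at 5.0 after a much larger rise does not. That inversion is specific to those two readings; the gap itself is not.

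**Does other text close the gap?** The Table 5 catch-all excludes laboratory values by its label. Section 16.2 speaks of grade 3 or higher but sends the reader back to Section 7.2 and adds no bilirubin threshold.

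**Does other text show what was intended?** Section 16.2 names grade 3 as the floor. The Table 11 note equates a sustained 50% rise from grade 2 with grade 3. Table 12 treats grade 3 and grade 4 bilirubin alike, so the exact upper limit of grade 3 does not matter here. Table 12's footnote attaches 5 x ULN to AST/ALT. Together these suggest a transaminase cut-off carried over to bilirubin.

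**Scale.** On the planned 40 evaluable patients, one reclassified patient is 1/40 = 2.5 percentage points. The toxicity denominator may differ from 40.

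**The case against.** The strongest reply is that this is a threshold preference. No sentence says that bilirubin above 3.0 x ULN must be a DLT, and Table 4 is selective elsewhere: platelets count only at grade 4, and kidney injury and proteinuria only if unresolved at 7 days. That is fair as far as it goes. But those rows state their choice openly, whereas the liver row sets its cut-off well above where it ends grade 2 and says nothing about a deliberate tolerance. With the Section 16.2 description and Table 12 beside it, an error is the better explanation.

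The limit to laboratory values also stands. A patient with bilirubin in the gap may still be a DLT through AST/ALT above 5 x ULN or through a related grade 3 clinical event.

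A reader might infer more than the documents support:

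- **That patients are unprotected.** They are not. Table 11 ("Elevation of liver enzymes or bilirubin") and Table 12 act on grade, not on the DLT label, and Section 16.3 still tabulates all grade 3 and 4 events.
- **That the lead-in or the safety stopping rule was compromised.** The label could matter in principle: with the plan's Beta(0.6, 1.4) prior, the posterior probability that the rate exceeds 40% is 0.920 at 4 of 5 and 0.725 at 3 of 5. But the documents report no bilirubin event in the gap, and Section 1.5 says the first 30 patients have been accrued.
- **That the Appendix H liver criteria show the DLT threshold to be too high.** Their stated purpose is to "specify a threshold of abnormal hepatic tests that may require an additional evaluation for an underlying etiology". A trigger for investigation may properly sit below a DLT threshold.
- **That the AST/ALT side is equally broken.** Taken literally, a patient with liver metastases at 4.8 x ULN becomes a DLT above 5 x ULN, a rise of 5/4.8 − 1 = 4.2%. This depends on applying the printed band to AST/ALT exactly as written, so it is secondary.
- **That the row should be rewritten.** Replacing its triggers could lose events that count now under reading (a), such as bilirubin from 2.0 to 6.0 x ULN resolving within 7 days, or from 4.0 to 5.5 (5.5/4.0 − 1 = 38%).

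**Conclusion.** The point holds in a narrow form. From a baseline of ≤1.5 x ULN, a related cycle 1 total bilirubin of >3.0–5.0 x ULN is not a DLT as a laboratory value on any of the four readings, and no other section repairs this. The conclusion rests on the closed list in Section 7.2 and on the row's own grade 2 ceiling; it needs no outside grading table.

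The consequence is a possible undercount of DLTs and, for a patient who leaves in cycle 1, loss of the DLT exception to the efficacy exclusion. How many patients are affected cannot be derived, because the documents give no bilirubin rate for this combination; that it is very small is a judgement. Few or no patients may remain to be treated: 10 expansion patients at one every 2 months take 10 × 2 = 20 months, and the latest dated revision (April 2020) comes 25 months after the March 2018 amendment that opened the expansion. The main value of a correction is therefore a correctly labelled DLT report. That justifies a wording change, but not reopening past decisions.

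**What to change.** Leave every existing liver trigger in Table 4 and add one separate line: total bilirubin >3.0 x ULN when baseline is ≤1.5 x ULN. State that the >5 x ULN cut-off and the 50% rule otherwise stand. Do not alter the Table 11 note or any dose-management rule.

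Apply the line to any patients still to be treated. Report the DLT count under the original definition as primary and with the added line as supplementary. The reasons for exclusion that Section 16.2 already requires would show any patient who left in cycle 1 for such a value.

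The cost is protocol wording and a re-read of existing results. The metabolic panel and direct bilirubin are already scheduled on days 1, 8, 15, 22, 29, 36 and 43 of cycle 1 and on cycle 2 day 1 (Section 12.2), so no new test is needed. The DLT count may rise slightly, and the supplementary count is post hoc for patients already treated. Some unevenness stays: under readings (a) and (d), 2.0 to 3.0 x ULN unresolved at 7 days counts and 1.0 to 3.0 does not. The second value, however, does not pass the row's own grade 2 ceiling.
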